Subjects who experience a flare or subjects who cannot adhere to the protocol-defined steroid taper due to a flare should be managed to ensure the best possible care of the subject. The subject must discontinue the assigned study drug (KPL-301 or placebo) and should receive escape therapy in accordance with local SoC, which may include, for example, dose modifications of corticosteroids, other immunomodulatory agents, and/or approved therapies (e.g. tocilizumab). Escape corticosteroid therapy can be escalated immediately. Due to possible safety and pharmacologic effects resulting from overlapping exposures to immunomodulatory agents on top of coadministered corticosteroids, the investigator should consider a washout period of at least 35 days (based on elimination half-lives) after the last dose of study drug if deemed clinically appropriate. The dosages of all concomitant medications used to treat the GCA flare must be entered into the eCRF.

Any subject who prematurely discontinues the study drug treatment for safety or other reason will have an EOT visit and will be followed for the intended duration of study treatment (i.e., through Week 26 and Washout Safety Follow-up) to address potential issues of informative censoring. Any subject who withdraws consent from the trial (i.e., all study procedures in addition to study drug) must complete at a minimum the Final Washout Safety Follow-up visit 84 ± 3 days from the last dose administered. Additional follow-up using public records may be captured where possible.

An analysis of the study will be performed when the last subject reaches Week 26 according to the SAP.

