14.1.1 Handling Dropouts and Missing Data

Criteria for removal of subjects from therapy or assessments are explained in [Section 8.8](#). Subjects who discontinue will not be replaced. To the extent possible, attempts will be made to minimize the amount of missing data through measures planned in the study conduct. Unless otherwise specified, missing data will not be imputed and only the observed data will be used in the analyses.

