## **5.2. Methods for Handling Missing Data**

Refer to Section 9 for detailed date imputation guidelines.

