### 6.6.2. Cumulative Dose

Cumulative dose (mg) is defined as sum of all doses taken. The dosage will be counted as 0 for days when the drug is not taken/injected. It will be calculated for study drug, prednisone taper, and steroid respectively. Cumulative study drug and prednisone taper will be calculated during treatment period. Cumulative steroid doses will be calculated at the end of week 26 and at the end of the safety follow up.

For the study drug, one partial injection is considered half of the full dosage.

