### 6.7.3. Analysis of Secondary Efficacy Endpoints

All analyses of secondary efficacy endpoints will use the mITT population. Sustained remission rate will be based on the adjudication outcome. Local assessments of ESR, CRP, and imaging will be used for other secondary efficacy endpoints.

#### 6.7.3.1. Sustained remission rate at Week 26

Subjects who complete the treatment period without a flare by week 26 will be considered to have sustained remission. The sustained remission rate at week 26 can be obtained from the estimates of time to flare at week 26 by using the Kaplan-Meier method, along with their standard errors using Greenwood's formula. Comparison with p-value will be conducted between the treatment groups. Two-sided p-value and 95% CI calculated using normal approximation.

#### 6.7.3.2. Time to elevated ESR by week 26

Time to elevated ESR will be defined as the time from randomization to earliest date of an ESR value of  $\geq 30$  mm/hr. All subjects who do not have an elevated ESR by week 26/ EOT will be censored at last assessment date or the randomization date, whichever is later.

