#### **6.7.3.5. *Cumulative steroid dose at Week 26 and at the End of the Washout Safety Follow-up Period***

The cumulative corticosteroid dose from first dose date of study drug to Week 26 will be compared between the treatment descriptively, and analytically using analysis of covariance (ANCOVA). The stratification factor and the corticosteroid starting dose will be the covariates in the model for treatment comparisons. The analyses will include 95% CIs for the difference of the mean cumulative steroid doses between the treatment groups.

Similar analysis will be conducted for cumulative steroid dose from first dose date to the end of the washout safety follow up period.

The average daily dose during the same periods will be summarized descriptively.

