#### **6.7.3.6. *Percentage of subjects who have completed the corticosteroid taper and who have a normal ESR by week 26***

The number and percentage of subjects who completed the corticosteroid taper per schedule and have normal ESR ( $< 30$  mm/hr) by week 26 will be presented by treatment. Subjects will be considered to have completed the corticosteroid taper if receiving 1 mg/day for those start at 60 mg/day starting dose, or 0 mg/day for those start with doses less than 60 mg/day by week 26 and maintain through week 26. Having normal ESR by week 26 requires all assessments of ESR from the completion of corticosteroid taper through week 26 being normal. If there is no assessment after completion of taper, the subject will not be counted in the numerator.

The percentage will be compared between the treatment groups using a Cochran-Mantel-Haenszel test controlling for the stratification factor; the 95% confidence interval for the difference of percentages will be displayed using the Mantel-Haenszel weight for the stratification factor.

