## 9. APPENDICES

### 9.1. Handling of Missing Safety Data

No imputation will be made for completely missing date unless otherwise specified. General imputation rules mentioned below apply to partially missing or impossible dates:

- If the stop date is not missing, and the imputed start date is after the stop date, the start date will be imputed by the stop date
- If the start date is not missing, and the imputed stop date is before the start date, then the imputed stop date will be equal to the start date
- Any imputed dates need to be logical. For example, last dose date should not be later than death date.

When imputation rules in subsequent sections contradicts the general rule, always follow the general rule.

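### Cumulative steroid dose: with a plain sum and no imputation, days after a subject leaves the study naturally add 0 mg, so an early leaver looks steroid-sparing

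*SAP*

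**What the plan says.** - **Definition.** SAP 6.6.2 makes cumulative dose a plain sum of doses taken: "The dosage will be counted as 0 for days when the drug is not taken/injected". The steroid total is taken at the end of Week 26 and at the end of safety follow-up. SAP 6.6 says it combines the prednisone taper and escape therapy.
- **Analysis.** SAP 6.7.3.5: "The cumulative corticosteroid dose from first dose date of study drug to Week 26 will be compared between the treatment descriptively, and analytically" by ANCOVA. The covariates are the stratum and the starting dose. The Week 38 total is treated in the same way.
- **Population.** SAP 6.7.3: "All analyses of secondary efficacy endpoints will use the mITT population". One dose and one assessment are enough for entry to that set, so early leavers are included.
- **Missing data.** SAP 5.2 says only: "Refer to Section 9 for detailed date imputation guidelines". The visible appendix, SAP 9.1, is titled "Handling of Missing Safety Data" and deals with dates. Protocol 14.1.1 gives the general default: "Unless otherwise specified, missing data will not be imputed and only the observed data will be used in the analyses".
- **Other tested endpoints.** The time-to-event endpoints and sustained remission rest on censoring rules (SAP 6.7.2 to 6.7.3.4). For the taper percentages, SAP 6.7.3.6 states: "If there is no assessment after completion of taper, the subject will not be counted in the numerator".
- **Follow-up.** Under Protocol 8.4.1, a subject who only stops study drug "will be followed for the intended duration of study treatment (i.e., through Week 26 and Washout Safety Follow-up". Protocol 8.4.1, 8.8 and 11.2 also ask subjects who withdraw consent for at least a final visit; 8.8 and 11.2 add an EOT visit and the washout period.

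**The concern.** The sum does not separate a day known to be steroid-free from a day on which nobody knows what was taken. Once contact ends, both add 0 mg, and a short record looks like a low steroid requirement.

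The effect on cumulative steroid dose is a stated secondary objective (SAP 1.1.2), and the two time points stand fifth and ninth in the ordered test list (SAP 3.2). Two distortions are possible:

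- Flare-free exits lower the mean of whichever arm loses more subjects.
- Exits at a flare hide the escape steroid that would have followed. Because the plan expects more flares on placebo, this shrinks a true difference.

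Study exit is foreseen: SAP 6.2 tabulates early termination, including loss to follow-up and withdrawal by the subject.

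**Working it through.** **Plan figures.** The documents give no size or power for cumulative dose, so there is no figure of that kind to reproduce. The flare assumptions used below come from SAP 1.3 and do reproduce: HR = ln(0.85)/ln(0.50) = 0.234, and expected events = 28 × 0.50 + 42 × 0.15 = 20.3, against about 20 required.

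**Scheduled totals.** Protocol Table 3, weekly daily dose × 7, summed over 26 weeks. For starts of 60, 50, 40, 35, 30, 25 and 20 mg the totals are 2,712.5, 2,292.5, 1,942.5, 1,662.5, 1,417.5, 1,347.5 and 1,312.5 mg. With an equal mix of starts (an assumption) the mean is 1,812.5 mg.

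**Flare-free exit, no later contact.** Omitted dose = scheduled total minus the sum to the exit week.

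| Exit after | Omitted, range over starts (mg) | Mean (mg) | Mean / 1,812.5 |
|---|---|---|---|
| Week 4 | 770 to 1,417.5 | 980 | 54% |
| Week 8 | 420 to 770 | 537.5 | 30% |
| Week 12 | 210 to 420 | 280 | 15% |

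**Shift from one Week 4 exit.** KPL-301: 980/42 = 23.3 mg (1.3% of 1,812.5). Placebo: 980/28 = 35.0 mg (1.9%).

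**If the final visit recovers the doses.** 84 days after a last study-drug dose at Week 4, 8 or 12 is Week 16, 20 or 24. The scheduled dose left after those weeks is 84 to 210, 14 to 84 and 0 to 14 mg. Table 1 counts the 84 days from the EOT visit instead; a later visit would leave no more than this.

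**Loss at flare (illustration only).** Assumptions: flare-free rates of 85% and 50%, exponential flare times, an equal mix of starts, daily sums over 182 days, and the same fraction *p* of flaring subjects leaving at flare in each arm. The escape courses are arithmetic devices, not proposals: linear from 30 to 10 mg over 10 weeks, 40 to 10 over 12, or 60 to 10 over 12, then held.

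Let E be the arm difference in escape dose from flare to Week 26, and R the arm difference in the scheduled taper that it replaces (about 193 mg). The full-data difference is D = E − R. If later days score 0 mg, the observed difference is (1 − *p*)E − R, so the shrinkage is *p*E/D.

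| Course | D (mg) | E = D + R (mg) | E/D | *p* = 5% | 10% | 20% |
|---|---|---|---|---|---|---|
| 30 to 10 | 400 | 593 | 1.48 | 7.4% | 14.8% | 29.7% |
| 40 to 10 | 571 | 764 | 1.34 | 6.7% | 13.4% | 26.8% |
| 60 to 10 | 836 | 1,029 | 1.23 | 6.2% | 12.3% | 24.6% |

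If the lost days are filled with the scheduled taper instead, the observed difference is (1 − *p*)(E − R). The shrinkage is then exactly *p*: 5%, 10% or 20%.

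**The case against.** The plan is not silent. Protocol 14.1.1 is a general rule for dropouts, and with a plain sum it gives a computable answer. That is correct, but the answer it gives is the problem: observed doses only, summed to a fixed week, is the same as 0 mg after exit.

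One can also argue that a day on which drug was not taken differs from a day on which intake is unknown, so an incomplete total should be missing and the subject dropped from the ANCOVA. The SAP does not say this, and it would select subjects on follow-up.

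Part of the SAP after Section 9.1.1 is not in the text available for review, so a dosing rule there cannot be excluded. The claim is limited to the visible text.

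The affected group may be small. Subjects who flare or stop study drug stay in follow-up, and doses used to treat a flare go into the eCRF. Withdrawers have visits at which doses could be recovered. All of this stands and keeps the severity down.

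A reader might infer a dropout rate from the increase from 60 to 70 subjects, which Amendment 4.0 explains by potential early dropout. The documents do not support that: under the plan's own rates, 70 subjects with no dropout yield 20.3 events against about 20 needed, so the increase leaves no visible margin.

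**Conclusion.** The concern holds in limited form, at minor to moderate severity. As written, the plan most naturally gives an early leaver a falsely low steroid total on two tested secondary endpoints.

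The per-subject effect can be large (on average 54% of the scheduled total for an uncontacted Week 4 exit), but one such exit moves an arm mean by only 1.3% to 1.9%. Loss at flare would shrink a true difference by about 6 to 7%, 12 to 15% or 25 to 30% at assumed losses of 5%, 10% or 20% of flaring subjects. Those figures depend on the assumed loss and the assumed escape courses.

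Three stronger readings are tempting and not supported:

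- That the rule favours KPL-301. No dropout rate is given, overall or by arm, so direction and net size are unknown.
- That everyone who stops treatment is affected. Only unrecovered time after study exit is.
- That a bound exists for Week 38. Protocol 8.4.2 leaves steroid use in Weeks 27 to 38 to the investigator and allows increases, so the documents give no schedule to measure against.

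**What to change.** In SAP 6.6.2 and 6.7.3.5:

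1. Count 0 mg only for days documented as zero dose within the observed steroid record. Include in that record doses recovered at the EOT, washout or final visit.
2. Treat days after the record ends, before Week 26 or Week 38, as missing.
3. Impute them with one fully pre-specified model that always includes arm, starting dose, stratum and flare status up to exit.
4. Report the number of incomplete records and the days missing, by arm.
5. Add two sensitivity analyses: the plain sum as now written and, to Week 26 only, filling with the scheduled taper. State that taper filling is not a bound after a flare.

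The cost is SAP wording and some programming, with no change to data collection. The downside is that the result then rests on an imputation assumption with few donors: 0.15 × 42 = about 6 expected flares on KPL-301 and 0.50 × 28 = 14 on placebo, before any loss. The choice should be fixed before unblinding.

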### 6.6.3. Average Daily Dose

Average daily dose (mg) is defined as the cumulative dose divided by the number of days dosed. This will be summarized for cumulative steroid dose.

#### **6.6.4. KPL-301/Placebo Exposure**

KPL-301 or placebo study drug exposure data will be summarized with descriptive statistics by treatment, and by treatment by randomization strata.

Summary statistics of study drug for the treatment duration (weeks) and number of injections will be presented. Number of injections by category (<10, 10-13, 14, >14) will be summarized by frequency and percent of subjects.

All KPL-301 exposure data will be listed.

#### **6.6.5. Prednisone Exposure**

Prednisone taper data will be summarized descriptively by treatment, and by treatment by randomization strata.

Summary statistics of prednisone for the treatment duration (weeks) and cumulative dose by earlier of flare and week 26 will be presented. Categorical summaries for prednisone starting dose (20mg, 25mg, 30mg, 35mg, 40mg, 50mg, 60mg) will be presented by treatment group.

All prednisone exposure data will be listed.

#### **6.6.6. Escape Therapy Exposure**

The number and percent of subjects receiving escape therapy, type of escape therapy and initial dose received will be summarized by treatment, and by treatment by randomization strata.

#### **6.6.7. Compliance**

Compliance to KPL-301/Placebo = Actual total number of injections received / planned total number of injections.

Compliance to prednisone will be measured by percentage of days in compliance = number of days in compliance / number of days on treatment. Descriptive summary will be presented for overall period and by week.

### **6.7. Efficacy Analysis**

All efficacy analyses will be conducted by treatment for the mITT analysis set. Selected analyses may be in the PP analysis set. Endpoints involving flare will be based on adjudication primarily. Investigator assessment will only be used supportively.

#### **6.7.1. Multiplicity Adjustment**

Multiplicity adjustment with respect to the primary efficacy and secondary efficacy endpoints will be adjusted using the gate-keeping hierarchical testing procedure. The hierarchy order of the secondary endpoints is presented in Section 3.2. For each endpoint, the null hypothesis is that there is no treatment difference between KPL-301 and placebo. The alternative hypothesis is that KPL-301 is superior to placebo. For each test, the 2-sided type I error rate is 0.05. The primary endpoint will be tested first. If the 2-sided p-value is  $\leq 0.05$ , statistical significance of the primary endpoint will be claimed, and the next hierarchical endpoint will be tested. This process will continue until an endpoint is not statistically significant.

There is no adjustment for other endpoints.

### 6.7.2. Analysis of Primary Efficacy Endpoint

The primary endpoint of time to flare by Week 26, is defined as time from randomization to the first flare occurring within the treatment period. Flare/relapse is defined as a C-reactive protein (CRP) of 1 mg/dL or greater and/or erythrocyte sedimentation rate (ESR) of 30 mm/h or greater AND at least one of the following signs or symptoms attributed to GCA:

- Cranial symptoms
  - New-onset localized headache
  - Scalp or temporal artery tenderness
  - Ischemic-related vision loss
  - Unexplained mouth or jaw pain upon mastication (i.e. claudication of tongue)
  - Transient ischemic aattach or stroke related to GCA
- Extracranial symptoms
  - Claudication of the extremities
  - Symptoms of PMR (shoulder & hip girdle pain associated with inflammatory morning stiffness)
- New or worsening angiographic abnormalities detected via MRI, CT/CTA, or PET-CT of the aorta or other great vessels or via ultrasound of the temporal arteries.

Supportive findings could include other symptoms related to worsening GCA, such as sustained daily recurrent fever with a temperature over 38°C for more than 1 week, chronic anemia, or unexplained weight loss.

Subjects who do not experience a flare during this period will be censored according to [Table 1](#) End of treatment (EOT) in the table refers to early discontinuation of treatment.

